Statistical Analysis Plan (SAP) – Primary Analysis (APHAB)

Project: Evaluation of Unilateral vs Bilateral Hearing Aids for the Treatment of Age-related Hearing Loss

IRB Number: Pro00106077

Investigator(s): [name], AuD, PhD

Biostatistician(s): [REDACTED]

Original Creation Date: 09.21.2021

Version Date: 11.13.2024

Investigator Agreement

- All statistical analyses included in an abstract or manuscript should reflect the work of the biostatistician(s) listed on this SAP. No changes or additional analyses should be made to the results or findings without discussing with the project biostatistician(s).
- All biostatisticians on this SAP should be given sufficient time to review the full presentation, abstract, manuscript, or grant and be included as co-authors on any abstract or manuscript resulting from the analyses.
- If substantial additional analysis is necessary or the aims of the project change, a new SAP will need to be developed.
- Publications resulting from this SAP are supported in part by the Duke CTSA and must cite grant number UL1TR002553 and be submitted to PubMed Central.
- I have reviewed the SAP and understand that any changes must be documented.

Acknowledged by: Click or tap here to enter text.

Date: Click or tap to enter a date.

Activity Log

- 10.07.2021 Moved 6 month APHAB outcomes to separate SAP and edited based on feedback/comments in the 09.21.2021_SBP SAP.
- 11.01.2021 Added written models
- 01.20.2022 Edited document based on discussions
- 07.20.2022 Stratified Table 1 by randomization
- 11.17.2022 Added additional details to variables
- 12.15.2022 Edited based on discussions
- 06.28.2023 Refined ITT language
- 05.31.2024 Updated audiogram data information
- 07.11.2024 Added specific subgroup analysis (mild vs moderate)
- 09.30.2024 Added APHAB subscale change scores, specified primary analysis as “completers” analysis, changed benefit scores to change scores (3m-baseline), updated variable names, added information about adjusted models/subgroup models
- 10.28.2024 Added ineligible (missing) definition to binary APHAB change score in Section 3.2, date of data lock

11.13.2024 Moved tables to different order, removed tables for analyses we are not doing/created a subsection describing which analyses we are not doing, updated heterogeneity of treatment effects to only mention variables of interest, added variables of interest for multiple imputation

Acronyms	APHAB	Abbreviated Profile of Hearing Aid Benefit

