1.2 Secondary Aims

- Compare the APHAB change scores between the two arms at the end of month 3 while adjusting for covariates
- Compare the APHAB change scores between the two arms at the end of month 3 with subgroup analyses
- Sensitivity analysis with missing data
- Analyze APHAB binary response at 3 months
- Create descriptives for the 4 APHAB subscales in unaided (baseline) and aided conditions (3 month) for each arm

2 Study Population

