2.3 Data Acquisition

Fill in all relevant information:

Study design	Randomized controlled trial with 2 arms (bilateral hearing aid, unilateral hearing aid) Note: Randomization was stratified by clinical site.
Data source/how the data were collected	Screening information pulled from EHR data Baseline surveys captured via in-person interview and recorded in REDCap
Contact information for team member responsible for data collection/acquisition	All data access is through [REDACTED] [REDACTED]. Questions on data validity will go to PI: [name] ([contact])
Date or version (if downloaded, provide date)	Date of data pull (locked data): 10/17/2024
Data transfer method and date	Direct data extraction from REDCap
Where dataset is stored	REDCap Extracted data and analytic datasets will be stored in a secure drive on the CRU folder. Path name: \\duhs-vclin-nc1\dusom_biostats_fs\Data\BiostatsCore\CRU\Head and Neck\[name]\PCORI_Pro00106077\Data pulls

Notes: Additional variable details for all variables can be found in the "PCORI Variable Details" Excel file. Scoring details for APHAB can be found in "PCORI Scoring 20240923".

Description:

3 Outcomes, Exposures, and Additional Variables of Interest

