3.3 Additional Variables of Interest

Variable	Description	Variables and Source	Specifications
Randomization assignment	Hearing aid assignment	assign	Binary 1: unilateral 2: bilateral
Clinical site	Which site - Duke or Vanderbilt?	which_site Character version: which_site_ch	Binary 1: Vanderbilt 2: Duke
Gender		gender Character version: gender_ch	Categorical 
 • 1: male • 2: female • 3: other • 99: declined
Age	Age at baseline (years)	age_base	Continuous

		Baseline visit is baseline_date	Years from baseline_date to dob Baseline visit is defined as aphab_base_date if non-missing, otherwise use date_moca
Race		race Character version: race_ch	Categorical 
 • 1: African American/Black • 2: White/Caucasian • 3: Asian • 4: Native American/Alaska Native • 5: Native Hawaiian/Pacific Islander • 6: More than one race • 99: Declined 
If cell counts are less than 10 for a given category, we may not report the exact cell count.
 
NIH racial categories: -American Indian/Alaska Native -Asian or Asian American -Black or African American -Native Hawaiian/Pacific Islander -White

Ethnicity		ethnicity Character version: ethnicity_ch	Categorical 
 • 1: Hispanic or Latino • 2: Not Hispanic or Latino • 999: Declined 
If cell counts are less than 10 for a given category, we may not report the exact cell count.

Income	Personal Income Last Year	income Character version: income_ch	Categorical 
 • 0: \$0 • 1: \$1 to \$9999 • 2: \$10,000 to \$24,999 • 3: \$25,000 to \$49,999 • 4: \$50,000 to \$74,999

			
 • 5: \$75,000 to \$99,999 • 6: \$100,000 to \$149,999 • 7: \$150,000 or greater • 999: Prefer not to answer 
We will also simplify this to below median/above median/prefer not to answer for heterogeneity of treatment effects

Hearing Aid Health Insurance Benefits		benefits Character version: benefits_ch	Categorical 
 • 0: No • 1: Yes • 998: Not Sure
Marital Status		marital Character version: marital_ch	Categorical 
 • 1: married • 2: widowed • 3: divorced • 4: separated • 5: never married • 999: prefer not to answer
Living arrangements		living Character version: living_ch	Categorical 
 • 1: alone • 2: with spouse • 3: with spouse and others • 888: other • 999: prefer not to answer

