4.3 Primary aim: compare APHAB scores between the two arms

Compare the APHAB change scores between the two arms (bilateral hearing aid and unilateral hearing aid) at the end of month 3 vs baseline.

Analysis: This will be done for all randomized patients who have both baseline and 3 month scores (a “completers” analysis). The primary analysis will be performed by linear regression and include randomized assignment and clinical site as covariates.

$$APHAB \text{ change score} = \beta_0 + \beta_1 * \text{treatment} + \beta_2 * \text{site}$$

Table 3: Linear Regression Beta Estimates
Outcome Modelled: APHAB Change Score

Covariate	Beta	95% C.I.	P-Value*
Hearing Aid Assignment (Reference: Bilateral)			
Unilateral	XXX	(XXX , XXX)	XXX
Clinical Site (Reference: Duke)			
Vanderbilt	XXX	(XXX , XXX)	XXX

*Using XXX statistic

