4.8 Initially planned analyses that we will not do

We had initially planned to conduct adjusted analyses for the outcomes of global change score and both responder definitions. After reviewing cell counts of demographics at baseline and discussion, we decided that there are no variables of interest to include in an adjusted model.

Statistical Analysis Plan (SAP) – Secondary (3-Month) Outcomes and Descriptives

Project: Evaluation of Unilateral vs Bilateral Hearing Aids for the Treatment of Age-related Hearing Loss

IRB Number: Pro00106077

Investigator(s): [name], AuD, PhD

Biostatistician(s): [name], [name], [name]

Original Creation Date: 12.15.2021

Version Date: 09.30.2024

Investigator Agreement

- All statistical analyses included in an abstract or manuscript should reflect the work of the biostatistician(s) listed on this SAP. No changes or additional analyses should be made to the results or findings without discussing with the project biostatistician(s).
- All biostatisticians on this SAP should be given sufficient time to review the full presentation, abstract, manuscript, or grant and be included as co-authors on any abstract or manuscript resulting from the analyses.
- If substantial additional analysis is necessary or the aims of the project change, a new SAP will need to be developed.
- Publications resulting from this SAP are supported in part by the Duke CTSA and must cite grant number UL1TR002553 and be submitted to PubMed Central.
- I have reviewed the SAP and understand that any changes must be documented.

Acknowledged by: Click or tap here to enter text.

Date: Click or tap to enter a date.

Activity Log

- 11.16.2023 Split secondary outcomes SAP into multiple SAPs
- 05.31.2024 Added additional variables
- 07.11.2024 Resolved some questions about variables (see SAP dated 20240531 and Overview of All Planned Analysis dated 20240620)
- 07.25.2024 Moved GHABP from the GHABP/EMA SAP to this SAP
- 09.30.2024 Updated variable names, resolved comments from previous SAP dated 20240725)

Acronyms

APHAB	Abbreviated Profile of Hearing Aid Benefit
EMA	Ecological Momentary Assessment
GHABP	Glasgow Hearing Aid Benefit Profile
IOI-HA	International Outcomes Inventory for Hearing Aids
SADL	Satisfaction with Amplification in Daily Life
SSQ	Speech Spatial Qualities
HHIE	Hearing Handicap Inventory for Elderly

1 Study Overview

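### The covariate-adjusted month-3 APHAB comparison is still a stated secondary aim, but section 4.8 withdraws it for a reason that does not reach the numeric baseline variables

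*SAP*

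**What the plan says.** Section 1.2 (Secondary Aims) of the primary SAP, version 11.13.2024, lists this aim: "Compare the APHAB change scores between the two arms at the end of month 3 while adjusting for covariates".

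Section 4.8 of the same version says: "We had initially planned to conduct adjusted analyses for the outcomes of global change score and both responder definitions". It then gives the reason for not doing so: "After reviewing cell counts of demographics at baseline and discussion, we decided that there are no variables of interest to include in an adjusted model".

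The model that remains for the change score is in section 4.3: "The primary analysis will be performed by linear regression and include randomized assignment and clinical site as covariates". It is fitted to completers, that is, randomised patients with both a baseline and a 3-month score.

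Three entries date the change. Section 2.3 gives "Date of data pull (locked data): 10/17/2024". The activity log for 09.30.2024 includes "added information about adjusted models/subgroup models", and the log for 11.13.2024 includes "removed tables for analyses we are not doing/created a subsection describing which analyses we are not doing". The log is used here only for dates. Sections 1.2 and 4.8, which conflict, are both current text.

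**The concern.** Two current sections of one SAP disagree about whether a secondary aim will be carried out, and the reason given for dropping it does not fit all the variables that could have been used. Cell counts matter for categories such as race, ethnicity or marital status. They say nothing about a variable entered as a single continuous term.

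Three things are at stake. A stated aim will have no result. Some precision is lost in the change-score comparison, although the data to recover it have been collected. And a planned analysis was recorded as removed after lock with a rationale that a reader of the final report can easily question.

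**Working it through.** **1. Does any remaining analysis meet the aim?** The section 4.3 model contains assignment and site. It is the primary analysis, so the separate secondary aim must mean something beyond it, and 4.8 treats the adjusted analyses as distinct from it. The section 4.4 models add income group or hearing-loss class with a treatment interaction. They examine heterogeneity and do not give one covariate-adjusted treatment effect. Nothing left in section 4 meets the aim.

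**2. Dates.**
- Adjusted-model information logged: 30 September 2024, 17 days before lock.
- Data lock: 17 October 2024.
- Removal logged: 13 November 2024. From 17 to 31 October is 14 days, plus 13 days in November, giving 27 days after lock.

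**3. Does the stated reason reach these variables?**

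| Baseline variable | Form in the primary SAP | Use as a covariate elsewhere |
|---|---|---|
| APHAB global | mean of item scores (3.1) | imputation model, 4.5; switching SAP 4.3 |
| Age | continuous (3.3) | switching SAP 4.3 |
| Better-ear pure-tone average | mean over four frequencies (3.3) | switching SAP 4.3; cut at 40 as hearing-loss class in 4.4 and 4.6 |
| MoCA | continuous, 0 to 30 (3.3) | switching SAP 4.3 |

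None of these has cells to count. The switching SAP, which uses all four, is dated 11.26.2024, 13 days after the primary SAP version that found no variables to adjust for.

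**4. What adjustment could be worth in the linear model.** Inputs from the documents are SD 25 (SAP 3.1), 350 patients (Protocol section 6) and 1:1 allocation (Protocol section 4), hence 175 per arm. Assumptions are that the SD of 25 applies to the change score, that everyone completes, and that intervals are 95% two-sided. The documents give no derivation of 350. It equals the total for d = 0.3 at 80% power and two-sided 0.05 without dropout, and it is close to d = 0.35 at 90% power (344), so it is neither confirmed nor refuted. Nothing below depends on how it was derived.

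Half-width with no added covariates: 1.96 × 25 × √(2/175) = 5.24 units.

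If the added covariates explain a share R² of the remaining variance, the standard error falls by 1 − √(1 − R²):

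| Assumed R² | Reduction in SE | Half-width (units) |
|---|---|---|
| 5% | 2.5% | 5.11 |
| 10% | 5.1% | 4.97 |
| 20% | 10.6% | 4.69 |

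Baseline APHAB can be examined separately. If baseline and month-3 scores have equal variance and correlation ρ, adding baseline multiplies the change-score variance by (1 + ρ)/2. For assumed ρ of 0.3, 0.5 and 0.7 the factor is 0.65, 0.75 and 0.85. The residual SD is 20.2, 21.7 and 23.1, and the half-width is 4.22, 4.54 and 4.83 units. These correspond to R² of 35%, 25% and 15%.

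With 10% loss (158 per arm) the starting half-width is 5.51. The percentage reductions are unchanged.

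**5. Responder models.** The formula in step 4 does not carry over to the logistic models in 4.6. Adding covariates there changes the odds ratio being estimated and does not in general shrink its standard error.

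**The case against.** The strongest reply is that this is a mismatch in documentation which deleting one line from 1.2 would cure. The site-adjusted comparison is valid without further covariates. The withdrawal is disclosed under its own heading. The reason given is cell counts together with a discussion, so it cannot be shown that sparse cells were the only ground. Choosing covariates now is also a post-lock decision.

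Much of this stands. Leaving out covariates does not in itself bias a randomised comparison, and any new list must be labelled as post-lock. But the content of the discussion is not reported, so the only reason a reader can assess is one that does not fit. Deleting the aim would make the text consistent but would give up the precision.

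A reader might infer more than the documents support:
- **That the analysis was dropped because of the results.** The log dates the writing of the change, not the decision. The review described was of baseline demographics, and nothing shows that outcomes by arm were seen.
- **That this was the only protection against dropout.** Section 4.5 plans multiple imputation if more than 5% of 3-month scores are missing, a comparison of patients with and without scores, and dropout rates by arm.
- **That every month-3 APHAB result is affected.** Section 4.6 Analyses 1 and 3 keep eligible patients without a 3-month score as non-responders, and hearing-loss class enters models in 4.4 and 4.6.
- **That the covariates are complete for everyone.** Table 1 has rows for missing age, MoCA and pure-tone average, and section 3.3 sets non-numeric audiogram entries to missing.

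**Conclusion.** The point holds in a limited form. Sections 1.2 and 4.8 contradict each other, the stated reason does not cover numeric baseline variables, and as written the adjusted change-score aim will not be delivered. The removal was recorded 27 days after lock; no stronger statement about timing or motive is supported.

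The cost is precision in the completer change-score analysis. It is a 2.5% to 10.6% larger standard error reduction forgone if R² is 5% to 20%, and more if baseline APHAB correlates with the month-3 score only as assumed in the ρ = 0.3 and 0.5 cases. R² and ρ are assumptions, since the documents give neither. The gain is claimed for the linear model only. The primary result remains valid, but the matter should be put right before reporting.

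**What to change.** Replace the relevant part of 4.8 with wording such as:

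> *The secondary aim of an adjusted change-score comparison will be met by repeating the section 4.3 linear model with baseline APHAB, age, better-ear pure-tone average and MoCA added as continuous covariates, whatever their balance between arms. The estimate will be reported beside the primary result. This covariate list was specified after data lock. Missing age, pure-tone average or MoCA values will be replaced by the overall mean of that variable.*

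Baseline APHAB needs no missing-value rule here, because completers have it by definition. Section 4.8 should also give the date of the original decision and what the discussion concluded.

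Adjusted responder models are not needed, since the aim concerns change scores only. If they are run, report them as conditional odds ratios beside the unadjusted ones.

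The cost is one more linear model on data already collected and one more row or table. If the team still prefers not to adjust, the minimum is to remove the aim from 1.2 and report the deviation with its date and full reason.

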1.1 Aims for Secondary Outcomes

- Compare all outcomes between the two arms (bilateral hearing aid and unilateral hearing aid) at 3 months. The primary hypothesis is that bilateral hearing aids are superior to the unilateral hearing aids with respect to the overall patient-reported benefit.
- Descriptive tables for additional clinical variables at baseline and 3-months by assigned treatment
- Plots of hearing aid fit by assigned treatment

2 Study Population

2.1 Inclusion Criteria

- 50+ years of age
- Mild to moderate, symmetrical SNHL (symmetrical: < 20 dB between ears on average from 500-4000 Hz)
- Open-mindedness to unilateral or bilateral amplification
- No prior hearing aid experience
- Adequate literacy to complete questionnaires
- Willing to purchase study-specific hearing aid(s)

2.2 Exclusion Criteria

- Concerns for middle ear pathology
- Concerns for retrocochlear pathology
- Severe tinnitus as the reason for seeking amplification
- Co-morbid condition that would interfere with study (e.g., dementia, blindness, neurologic pathology)
- History of fluctuating hearing loss

2.3 Data Acquisition

Fill in all relevant information:

Study design	Randomized controlled trial with 2 arms (bilateral hearing aid, unilateral hearing aid) Note: Randomization was stratified by clinical site.
Data source/how the data were collected	Screening information pulled from EHR data Baseline surveys captured via in-person interview and recorded in REDCap
Contact information for team member responsible for data collection/acquisition	All data access is through [REDACTED] [REDACTED]. Questions on data validity will go to PI: [name] ([contact])
Date or version (if downloaded, provide date)	10.17.2024
Data transfer method and date	Direct data extraction from REDCap
Where dataset is stored	REDCap

	Extracted data and analytic datasets are stored on a secure drive in the CRU folder: \\duhs-vclin-nc1\dusom_biostats_fs\Data\BiostatsCore\CRU\Head and Neck\[name]\PCORI_Pro00106077\Data pulls
--	--

Notes: Additional variable details for all variables can be found in the “PCORI Variable Details” Excel file. Scoring details can be found in “PCORI Scoring 20240923”.

For GHABP:

6 total scenarios, 4 standard, 2 user-nominated. Standard scenarios:

1. LISTENING TO THE TELEVISION WITH OTHER FAMILY OR FRIENDS WHEN THE VOLUME IS ADJUSTED TO SUIT OTHER PEOPLE
2. HAVING A CONVERSATION WITH ONE OTHER PERSON WHEN THERE IS NO BACKGROUND NOISE
3. CARRYING ON A CONVERSATION IN A BUSY STREET OR SHOP
4. HAVING A CONVERSATION WITH SEVERAL PEOPLE IN A GROUP

Unaided questions:

1. Does this situation happen in your life?
2. How much difficulty do you have in this situation?
3. How much does any difficulty in this situation worry, annoy or upset you?

Aided/EMA questions:

1. Did this situation happen in the past few weeks? (GHABP aided) OR Did this situation happen in the last three hours? (EMA)
2. In this situation, with your hearing aid, how much does any difficulty in this situation worry, annoy or upset you? **NOTE: this question is non-standard for the aided GHABP.** We will report on this in a descriptive table but will not include in analyses.
3. In this situation, what proportion of the time do you wear your hearing aid?
4. In this situation, how much does your hearing aid help you?
5. In this situation, with your hearing aid, how much difficulty do you now have?
6. For this situation, how satisfied are you with your hearing aid?

Description:

3 Outcomes, Exposures, and Additional Variables of Interest

3.1 *Outcome(s)*

Outcome	Description	Variables and Source	Specifications
IOI-HA	Note: this is measured only at 3 and 6 months	Total score: ioiha_total_3m	Total score: sum responses to questions 1-7 (should be on a range between 1-5). Item 8 is self-perceived hearing difficulty used for normative purposes

			
(currently not used as part of total score)
 
This is initially coded as 0 to 4 in REDCap – changed to 1-5
 
Currently, we're treating IOI-HA total score as continuous, but this may need to be treated as ordinal.
 
Higher scores are better

SADL	
Note: this is measured only at 3 and 6 months.
 
Note: the “sister” questionnaire at baseline is ECHO
	
Global score: sadl_global_3m
 
Positive effect subscale: sadl_positive_effect_3m
 
Service cost subscale: sadl_service_cost_3m
 
Negative features subscale: sadl_negative_features_3m
 
Personal image subscale: sadl_personal_image_3m
	
Questions 1 – 15 are used. This is scored from 1-7 (or reversed for questions 2, 4, 7, 13).
 
There are 4 subscales: Positive Effect, Service & Cost, Negative Features, Personal Image. For each subscale, the average score is calculated.
 
For the global score, this is the mean of the scores for all items (excluding questions 11 and 14 if applicable).
 
Higher scores are better (higher satisfaction).
 
See PCORI Scoring file for more details

SSQ	
Note: this is measured at baseline, 3 months, and 6 months.
	
Change score: ssq_change
 
Baseline:
 
Overall score: ssq_overall_base
 
Speech/hearing subscale: ssq_speech_hearing_base
 
Spatial/hearing subscale: ssq_spatial_hearing_base
	
3 subscales: Speech is questions 1 – 14 (corresponds to the “pt1” variables). Spatial is 17 questions (corresponds to the “pt2” variables). Qualities is 18 questions (correspond to the “pt3” variables).

		
Qualities of hearing subscale: ssq_qualities_of_hearing_base
 
3-Months: Overall score: ssq_overall_3m
 
Speech/hearing subscale: ssq_speech_hearing_3m
 
Spatial/hearing subscale: ssq_spatial_hearing_3m
 
Qualities of hearing subscale: ssq_qualities_of_hearing_3m
	
Overall score: mean of the items.
 
For instances where people mark NA and a value, if the value is 50, set as NA. If a value other than 50, use that value.
 
We will also create a change score as the difference in the overall score between 3 months and baseline (3 months – baseline)
 
Higher scores are better

HHI-E	Note: this is measured at baseline, 3 months, and 6 months	
Change score: hhie_change
 
Baseline: Total score: hhie_total_base
 
Situational subscale: hhie_situational_base
 
Emotional subscale: hhie_emotional_base
 
3-Months: Total score: hhie_total_3m
 
Situational subscale: hhie_situational_3m
 
Emotional subscale: hhie_emotional_3m
	
Yes = 4 points, Sometimes = 2 points, and No = 0 points.
 
Total scale score = sum of all 25 items
 
Situational subscale: questions 1, 3, 6, 8, 10, 11 13, 15, 16, 19, 21, 23
 
Emotional subscale: questions 2, 4, 5, 7, 9, 12, 14, 17, 18, 20, 22, 24, 25
 
We will also create a change score as the difference in the total scale score between 3 months and baseline (3 months – baseline)
 
Lower scores are better

GHABP Aided	Aided: 3 months	
Question 2 average, 4 standard scenarios: ghabp_q2_4block_3m
 
Question 3 average, 4 standard scenarios: ghabp_q3_4block_3m
	
For questions 3-6 (IF they answer yes to question 1), doing this separately by question:
 
 1. Subtract 1, multiply by 25, average answer to question across

		
Question 4 average, 4 standard scenarios: ghabp_q4_4block_3m
 
Question 5 average, 4 standard scenarios: ghabp_q5_4block_3m
 
Question 6 average, 4 standard scenarios: ghabp_q6_4block_3m
	
4 standard scenarios
 
Note: ignore current question 2 for analyses as it is non-standard but report on this in a descriptive table
 
There are 6 scenarios (4 standard, 2 user-nominated)
 
Note that question 1 just asks if this scenario has happened – participants are only included in the averages if they answer “yes”
 
Higher/lower scores are better depending on question

Speech and Noise Test	
Baseline (unaided) and 3-months (aided)
 
Speech and noise 0 degrees (collocated)
 
Speech left, noise right
 
Noise left, speech right
	
Baseline:
 
sin_collocated_base sin_right_base sin_left_base
 
3-Months:
 
sin_collocated_3m sin_right_3m sin_left_3m
 
Change:
 
sin_collocated_change sin_r_change sin_l_change
 
May also want change scores for speech to aided side and speech to unaided side
	
Continuous
 
Change scores: 3m-baseline for each of collocated, speech left/noise right, noise left/speech right
 
Positive values for unaided/aided variables indicate speech is louder than noise; negative indicate speech is under the noise
 
For unilateral assigned, also have speech to aided side (advantage) and speech to unaided side (disadvantage).
 
Speech to aided (advantage):
 
 • If assigned R, this is noise left, speech right

			
 • If assigned L, this is speech left, noise right 
Speech to unaided (disadvantage):
 
 • If assigned R, this is speech left, noise right • If assigned L, this is noise left, speech right 
Lower scores are better

Auditory Working Memory	
Unaided and Aided (3 months)
 
Recognition, judgement, recall
	
Change scores: warrm_recog_change warrm_recall_change
 
Baseline: warrm_recog_base warrm_recall_base warrm_judge_base
 
3-Months: warrm_recog_3m warrm_recall_3m warrm_judge_3m
	
Continuous
 
Sum questions 2-6 for each tasks (recognition, judgement, recall) separately and get a % correct (out of 20)
 
Construct change scores as difference between 3 months and baseline for recognition and recall.
 
Judgement is more of a sanity check (<90% means they probably aren't engaged)
 
Higher scores are better

Hours of Hearing Aid Use	
Multiple time periods (every scheduled visit and unscheduled follow ups)
 
Only reporting 3-month values here
 
Right and left ears separately
	
Right ear: r_avg_hrs_3m r_avg_hrs_3m_na (if right HA is NA)
 
Left ear: l_avg_hrs_3m l_avg_hrs_3m_na
	
How many hours on average the right/left HA was worn.
 
NA variables: value of 1 if that HA was NA

